ENDPOINTS:

Primary Endpoint

- One point decrease from baseline in target lesion Global PG (GPG) Severity Score at Week 16

Secondary Endpoints

- Complete re-epithelization of PG lesions (GPG Severity Score of 0) at visits 3, 4, 5, 6, 7, 8, and 9.
- Absolute change from baseline in patient-reported pain severity (Pain-VAS) at visits 3, 4, 5, 6, 7, 8, and 9 and at complete re-epithelization of ulcer.
- Absolute change in quality of life (DLQI) from baseline at visits 3, 4, 5, 6, 7, 8, and 9 and at complete re-epithelization of ulcer.
- Recurrence of PG lesions after complete re-epithelization (GPG score 0) of all lesions and spesolimab cessation

- Time to worsening (1 or more GPG point increase) of target PG lesion from spesolimab cessation

STUDY DESIGN OVERVIEW:

This study is a prospective, proof-of-concept, open label clinical trial. The study will take place at Icahn School of Medicine at Mount Sinai.

The study will screen up to 25 subjects in order to enroll a total of up to 20 patients with at least one clinically measurable ulcerative PG lesion. Subjects will receive 900 mg of spesolimab intravenously (IV) over 90 minutes at a frequency of every 4 weeks until Week 28 with the following exceptions:

- At the Week 8 visit, subjects who do not show any improvement, show only minimal improvement, or those that begin to lose their initial improvement response (decrease in pain or wound drainage), may be switched to a dosing frequency of every 3 weeks through Week 26, at the discretion of the investigator. These subjects will still return at Week 16 for an endpoint visit, but will not receive treatment at this visit. Refer to Tables 3 and 4 for schedule of events.

All subjects will be monitored monthly for 4 months subsequent to treatment cessation.

Subjects who reach GPG score 0 at anytime during the study will continue to receive treatments until week 28 (or Week 26 depending on dosing frequency) and will then be monitored for 4 months subsequent to treatment cessation.

Subjects who are experiencing improvement in their PG but who have not reached complete wound healing will continue treatment until Week 28 (or Week 26 for those who were switched to every 3 week dosing), even if primary endpoint has been achieved. These subjects will then be monitored for 4 months subsequent to treatment cessation.

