Subjects who have not improved and not worsened significantly will also continue to receive treatments until week 28 (or Week 26 depending on dosing frequency) and will then be monitored for 4 months subsequent to treatment cessation.

Any subject that experiences significant worsening will be discontinued from the study.

After providing consent, subjects will be assessed for study eligibility during the screening period (within 28 days of baseline). The screening visit includes a review of the subject's past and current medical conditions as well as a review of family history of associated relevant diagnoses such as inflammatory bowel disease, rheumatoid arthritis, and hematological malignancy. Subjects will also be asked to review past surgical history and history of any relevant skin trauma. Subjects will also be asked to report past and current treatment regimens of their PG and their perception of response to each treatment trialed. A limited physical exam will be performed, vitals collected, blood samples collected for safety tests (including screenings for HIV, hepatitis B and C and tuberculosis), and the physician will assess number, location, and severity of PG lesions.

Subjects who meet inclusion criteria for eligibility will undergo Baseline assessments at Week 0, including clinical assessments, review of concomitant medications, limited physical examination, vitals, standardized clinical photography, questionnaires (patient PG questionnaire, pain VAS and DLQI). Blood samples (CBC, CMP, CRP, serum cytokine profiles, pharmacokinetics, Nab, ADA) will be collected to monitor for adverse effects of medication and overall inflammatory response.

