Contraindications to spesolimab treatment include patients with severe or life-threatening hypersensitivity to spesolimab or to any of the excipients in spesolimab¹⁴. In our experience, patients infused with spesolimab exhibited no adverse reactions during or after treatment with no pre-medication required. There is limited data available on the impact of antidrug antibodies on safety and efficacy upon retreatment. Furthermore, it is not known whether spesolimab increases or decreases the efficacy of other medications.

PRIOR TREATMENT:

All relevant treatment received by the subject within 30 days before screening will be recorded.

CONCOMITANT TREATMENT:

Concomitant medications are permitted for the treatment of stable, chronic illness as well as for pyoderma gangrenosum. Concomitant treatments for pyoderma gangrenosum will tapered over spesolimab treatment course as tolerated. Use of such concomitant medication or other medications that may be required throughout the study will be recorded (including the reason for treatment and name, dose, unit, route, and the date of treatment as appropriate) until treatment termination and throughout follow-up period. Patients will be allowed to continue with biologic therapies used to treat comorbidities.

PROHIBITED TREATMENT:

All treatments prohibited by clinician during the screening period are also prohibited throughout the course of the study. No live attenuated vaccinations are permitted throughout the study.

PROCEDURES:

Monitoring of AEs will begin at the time of signing the informed consent form and will be continued throughout the course of the study. All study procedures will be completed at designated times during the study period (see Tables 3 and 4). Subjects will receive 900mg IV spesolimab at a frequency of every 4 weeks through Week 8, at which time, at the discretion of the investigator, dosing frequency may be increased to every 3 weeks. Subjects will continue to dose every 4 or 3 weeks through Week 28 or 26 (depending on

dosing frequency). Subjects will be monitored once a month, for 4 months after treatment cessation. Patients that, in the opinion of the investigator, are benefiting from treatment at week 28 but need more therapy to achieve wound closure may be eligible to continue on treatment (on case-by-case basis) to a maximum of 52 week after discussion with Boehringer Ingelheim trial team.

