- Urine pregnancy test for all female subjects of child-bearing potential to confirm subject is not pregnant
- Collect blood samples for CBC with differential, CMP, and C-reactive protein (CRP), serum cytokine profiling (O-link® inflammatory cytokine panel, IL-1 β , and IL-36 subtypes), Nab, ADA, and Pre- and post dose pharmacokinetics.
- Administer study drug

Spesolimab Treatment Phase

Visits 3 thru 9 (subjects that dose every 4 weeks) or Visits 3 thru 11 (subjects that are switched to every 3 week dosing at Week 8)

- Record concomitant medications (including use of pain medication) and adverse events
- Urine pregnancy test for all female subjects of child-bearing potential to confirm subject is not pregnant
- Patient Pyoderma Gangrenosum Questionnaires and DLQI
- Obtain vital signs
- Standardized clinical photography of target lesion and other PG lesions
- PG clinical assessments (including number/location/measurements of PG lesions and GPG score for target lesion)
- Assess status of associated comorbid conditions (improved, no change, worse)
- Collect blood samples for CBC with differential, CMP, and C-reactive protein (CRP)
- **Only at Week 8 and Week 28 (subjects dosed every 4 weeks) or Week 26 (subjects switched to dosing every 3 weeks):** Nab, ADA, and pre dose pharmacokinetics.
- **Only at Week 16:** serum cytokine profiling (O-link® inflammatory cytokine panel, IL-1 β , and IL-36 subtypes), Nab, ADA, and pre dose pharmacokinetics.
- Administer study drug

Post-Spesolimab Follow-up Phase

Visits 10 thru 13 (subjects dosed every 4 weeks) or Visits 12-15 (subjects switched to dosing every 3 weeks)

Follow-Up Visits at 1 Month, 2 Months, 3 Months and 4 Months Post-Spesolimab Treatment Cessation

- Record concomitant medications (including use of pain medication) and adverse events
- Patient Pyoderma Gangrenosum Questionnaires and DLQI
- Assess status of associated comorbid conditions (improved, same, worse)
- Standardized clinical photography of target lesion and other PG lesions

- PG clinical assessments (including number/location/measurements of PG lesions, and GPG score of target lesion)
- Collect blood for serum cytokine profiling (O-link® inflammatory cytokine panel, IL-1 β , and IL-36 subtypes)
- If subject worsens or sees progression of their PG during the 4- month follow-up period (defined as 1 or more increase in GPG score of target lesion), then patient will be discontinued from the study and started on available, standard PG therapies.

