
Early Termination Visit (if applicable)

- Record concomitant medications (including use of pain medication) and adverse events
- Urine pregnancy test for all female subjects of child-bearing potential to confirm subject is not pregnant
- Patient Pyoderma Gangrenosum Questionnaires and DLQI.
- Assess status of associated comorbid conditions (improved, same, worse)
- Obtain vital signs
- Standardized clinical photography of target lesion and other PG lesions
- PG clinical assessments (including number/location/measurements of PG lesions and GPG score of target lesion)
- Collect blood samples for CBC with differential, CMP, and C-reactive protein (CRP), and serum cytokine profiling (O-link® inflammatory cytokine panel, IL-1 β , and IL-36 subtypes)

SAFETY MONITORING:

The study will be conducted in accordance with our department's Standard Operating Procedures, which are based on US FDA Title 21 Code of Federal Regulations and ICH Good Clinical Practice guidelines. An investigator will review all laboratory results and assess for adverse events. The principal investigator will be informed of all adverse events. In the event that a subject's safety is compromised, the investigator will discontinue the subject immediately.

ADVERSE EVENT REPORTING:

Definitions of adverse events

Adverse event

An adverse event (AE) is defined as any untoward medical occurrence, including an exacerbation of a pre-existing condition, in a patient in a clinical investigation who received a pharmaceutical product. The event does not necessarily have to have a causal relationship with this treatment.

An AE can therefore be any unfavorable and unintended sign (including an abnormal laboratory finding), symptom, or disease temporally associated with the use of a medicinal product, whether or not considered related to the medicinal product.

The following should also be recorded as an AE in the CRF and BI SAE form (if applicable):

- Worsening of the underlying disease or of other pre-existing conditions

- Changes in vital signs, physical examination and laboratory test results, if they are judged clinically relevant by the investigator.

Serious adverse event

A serious adverse event (SAE) is defined as any AE, which fulfils at least one of the following criteria:

- results in death,

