- Additional arguments amongst those stated before, like alternative explanation (e.g. situations where other drugs or underlying diseases appear to provide a more likely explanation for the observed event than the drug concerned).
- Disappearance of the event even though the trial drug treatment continues or remains unchanged.

Responsibilities for SAE reporting to Boehringer-Ingelheim (BI)

The Sponsor shall report (i.e., from signing the informed consent onwards through the protocol specified follow-up period after discontinuing spesolimab) all SAEs and non-serious AEs which are relevant for a reported SAE and Adverse Events of Special Interest (AESI) by fax or other secure method using BI IIS SAE form to the BI Unique Entry Point in accordance with timeline specified in the Safety Data Exchange Agreement.

BI Unique Entry point for SAE/AESI reporting:

[contact]

SAE/AESI reporting timelines

- within five (5) calendar days upon receipt of initial and follow-up SAEs containing at least one fatal or immediately life-threatening event;
- within ten (10) calendar days upon receipt of any other initial and follow-up SAEs and AESIs.

For each adverse event, the investigator will provide the onset date, end date, intensity, treatment required, outcome, seriousness, causality and action taken with the BI study drug. The investigator will determine the expectedness of the investigational drug to the AEs as defined in the Listed Adverse Events section of the Boehringer Ingelheim's (BI's) Investigator Brochure for the Product or Product Information (PI) for the authorized Study Drug provided by BI.

The investigator does not need to actively monitor patients for adverse events once the clinical trial has ended. However, if the investigator becomes aware of an SAE(s) that occurred after the patient has completed the clinical trial (including any protocol specified follow-up period), it should be reported to BI if investigator considers it as relevant to the BI study drug.

Pregnancy

In the rare case that a female subject participating in this clinical trial becomes pregnant after having taken trial medication, the Investigator must report immediately (within 24 hours) the drug exposure during pregnancy (DEDP) to the Sponsor's unique entry point. The Pregnancy Monitoring Form for Studies (Part A) should be used.

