The outcome of the pregnancy associated with the drug exposure during pregnancy must be followed up and reported to the Sponsor's unique entry point on the Pregnancy Monitoring Form for Studies (Part B).

As pregnancy itself is not to be reported as an AE, in the absence of an accompanying SAE and/or AESI, only the Pregnancy Monitoring Form for Studies and not the SAE form is to be completed. If there is an SAE and/or AESI associated with the pregnancy an SAE form must be completed in addition.

STUDY WITHDRAWAL:

In the event a study subject wants to withdraw early from the study for any reason, the subject will be asked to return for an Early Termination visit (see above for procedures).

Table 2: TOTAL VOLUME OF BLOOD COLLECTED DURING THE STUDY:

		Treatment				Follow-Up
Visit	1 Screening	2 Baseline	3, 5, 7, 8, 9	4	6	10-13

Blood + Serum	23	32	15	20	23	23
Total volume	23	23	15	20	23	23

The total estimated blood volume is between 15 and 23 mL per month during treatment, and 23 mL per month during Follow-Up period. Additional volumes may be required for repeat testing or as part of unscheduled visits.

DISCONTINUATION OF TREATMENT AND WITHDRAWAL OF SUBJECTS:

The reasons why a subject may discontinue or be withdrawn from the study by the investigator include, but are not limited to the following: subject request, protocol violation, loss to follow up, subject non-compliance, significant worsening of subject's disease, study termination by investigators, and a confirmed grade 3 or higher adverse event (using Common Terminology Criteria for Adverse Events), which is suspected to be related to test article administration. Subjects that elect to withdraw from the trial due to lack of efficacy and/or exacerbation of disease will undergo an Early Termination visit (see Procedure Section and Schedule of Events)

Stopping Rules

Patients will be permanently discontinued from study treatment in the event of:

- Anaphylactic reaction or other severe systemic reaction to study drug injection
- Pregnancy at any time during the study period
- Diagnosis of a malignancy during study, excluding carcinoma in situ of the cervix, or squamous or basal cell carcinoma of the skin
- Treatment with any prohibited concomitant medication or procedure
- Any infection that is opportunistic, whose nature or course may suggest an immunocompromised status

Study drug dosing may be temporarily suspended in the event of:

- Intercurrent illnesses or major surgery

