Subjects are numbered sequentially. Each subject screened (total of 25 screened) will be assigned a unique screening number for the duration of the study. Subject screening numbers will also become a subjects treatment number if they are enrolled in the study after providing informed consent and meeting inclusion criteria. Subjects who discontinue or withdraw from the study before receiving a treatment assignment code, but re-enroll at a later time must be assigned a new screening number. The investigator must maintain a master log linking the subject number to the subject's name. The investigator must follow all applicable privacy laws in order to protect a subject's privacy and confidentiality.

INVESTIGATIONAL DRUG SUPPLY :

Eligible participants will receive 900 mg intravenous spesolimab starting at Visit 2/week 0/Baseline. All participants will receive a total of 8 or 9 infusions (depending on dosing frequency) through Week 28 or Week 26 (depending on whether the subject's dosing frequency is increased to every 3 weeks at Week 8), unless there is significant worsening. All subjects should be observed for 30 minutes following the infusion at Baseline to assess safety. Select cases will be offered the opportunity to continue treatment through Week 52 on case-by-case basis if the patient would benefit from continued treatment. All subjects who have not been discontinued will be monitored once a month, for 4 months after treatment cessation.

All study medication will be provided by Boehringer Ingelheim, refrigerated and stored between 2-8°C in a secure area. Study drug will be administered to subjects at each study visit in office. The investigative site will account for all study drug dispensed and stored during the study.

STATISTICAL CONSIDERATIONS:

Sample Size

This is a proof-of-concept, open-label trial. Twenty patients will be enrolled in the trial to demonstrate efficacy of spesolimab in a population of patients with moderate-severe, refractory PG. Although there is no formal power calculation, a sample size of n=20 subjects allows 81% power at 2.5% significance for a one-sided binomial test to detect at Week 16 a difference of 36.6% in the proportion of GPG success compared to a constant set to be equal to 10%. The choice of the constant was based on data from a randomized clinical trial for efficacy of infliximab where a group of 17 PG placebo-treated patients showed 6% response at Week 2 (Brooklyn et al.,2006).

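### The protocol gives conflicting rules on who is followed for 4 months after the last dose, and does not separate stopping spesolimab from leaving the study

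*Combined protocol and SAP*

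**What the plan says.** Two sections give a general rule. Study Design Overview says "All subjects will be monitored monthly for 4 months subsequent to treatment cessation", and Procedures says "Subjects will be monitored once a month, for 4 months after treatment cessation".

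Investigational Drug Supply is narrower: "All subjects who have not been discontinued will be monitored once a month, for 4 months after treatment cessation". It does not say whether being discontinued there means from the drug or from the study.

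Other sections remove subjects, in different terms:

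- Study Design Overview, worsening on treatment: "Any subject that experiences significant worsening will be discontinued from the study".
- Post-Spesolimab Follow-up Phase, target-lesion GPG score up by 1 or more: "then patient will be discontinued from the study and started on available, standard PG therapies".
- Safety Monitoring, when safety is compromised: "the investigator will discontinue the subject immediately". What the subject is discontinued from is not stated.
- Discontinuation of Treatment and Withdrawal of Subjects lists a confirmed, suspected-related adverse event of grade 3 or higher among the reasons to discontinue or be withdrawn from the study.
- Stopping Rules (anaphylaxis or other severe systemic reaction, pregnancy, malignancy, prohibited treatment, opportunistic infection): "Patients will be permanently discontinued from study treatment in the event of". Continued follow-up is not mentioned.

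The SAE and AESI reporting window to the drug manufacturer runs "from signing the informed consent onwards through the protocol specified follow-up period after discontinuing spesolimab".

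**The concern.** A site with a subject who stops early cannot tell from the protocol whether the four follow-up visits still apply. If they do not, scheduled adverse event collection ends sooner in subjects who worsened or were stopped for harm than in subjects who did well. The protocol's risk section lists serious or opportunistic infection, systemic hypersensitivity, malignancy and peripheral neuropathy as potential risks still under evaluation. Subjects with such events are among those likely to be stopped, so the loss would be related to outcome. The safety analysis tabulates adverse events by visit, and the follow-up columns would then describe mainly subjects who tolerated treatment and did not worsen.

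There is also a consequence for efficacy. A subject removed from the study before Week 16 has no GPG score at the primary time point, and Analysis of Primary Endpoint gives no rule for a missing value.

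**Working it through.** The documents give no figure for follow-up completeness to reproduce, so the check sets the rules side by side and counts the visits each one puts at risk.

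**1. Which rule reaches which subject**

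| Situation | Wording of the removal | Are the 4 follow-up visits due? |
|---|---|---|
| Completes treatment, no worsening | none | Yes, under every section |
| Significant worsening on treatment | leaves the study | No under Study Design Overview and Drug Supply, despite the general rule |
| GPG score up by 1 or more in follow-up | leaves the study | Not after the visit at which it is found |
| Related adverse event of grade 3 or higher | discontinue or be withdrawn from the study | Probably not, but no section says so directly |
| Anaphylaxis, malignancy, opportunistic infection, pregnancy | stops study treatment | Yes under Study Design Overview and Procedures; no if Drug Supply's limit includes stopping treatment |

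**2. Visits at risk per subject**

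Inputs: 4 follow-up visits, at 4, 8, 12 and 16 weeks after the last dose (Visits 10 to 13 in Table 3, Visits 12 to 15 in Table 4).

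- Removed from the study while on treatment: 4 − 0 = 4 visits, 16 weeks of scheduled observation.
- Removed at follow-up visit k: 4 − k visits and 16 − 4k weeks remain unobserved. For k = 1, 2, 3, 4 this is 3, 2, 1, 0 visits and 12, 8, 4, 0 weeks.
- Stops treatment only, with the general rule applied: 0 visits.

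**3. What still covers the gap**

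- *Early Termination visit.* One visit, with adverse events, vital signs, laboratory tests and GPG score. Study Withdrawal and the Discontinuation section require it of subjects who want or elect to withdraw. Its heading in Procedures says only that it is held if applicable. No section clearly requires it when the investigator discontinues the subject, and no scheduled visit follows it.
- *AESI follow-up.* Required, without duration or schedule.
- *SAE and AESI reporting.* The window ends with the protocol follow-up period, which is the period in dispute. After the trial has ended no active monitoring is required.
- *Routine adverse event monitoring.* Procedures continues it only for the course of the study.

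What remains uncovered is scheduled collection, mainly of non-serious events, after the subject leaves the study.

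**4. Why the Week 16 score matters (illustration)**

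Inputs from Sample Size: constant 10%, one-sided 2.5% level, n = 20. The exact p-value is P(X ≥ r) for X ~ Binomial(n, 0.10). Assume r = 5 responders, and assume 0 to 3 subjects are removed before Week 16 and left out of the denominator. Neither number comes from the documents.

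| Subjects left out | n analysed | P(X ≥ 5) |
|---|---|---|
| 0 | 20 | 0.043 |
| 1 | 19 | 0.035 |
| 2 | 18 | 0.028 |
| 3 | 17 | 0.022 |

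With these assumed counts the result crosses 2.5% at three exclusions. This does not predict the trial's result. It shows only that a few missing Week 16 scores can decide the primary test while their handling is unstated.

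**The case against.** The sections can be partly harmonised. Study Design Overview gives a general rule and an exception for significant worsening, and Drug Supply may simply restate the pair. The Stopping Rules end study treatment only, so subjects stopped for anaphylaxis, malignancy or opportunistic infection may still come under the general rule. This stands as a possible reading, but nothing in the text settles it.

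The safeguards are real. Anaphylaxis and opportunistic infection are AESIs and must be followed up, pregnancies are followed to outcome, and extra safety evaluations are allowed. A reader might infer that subjects stopped for harm have no planned follow-up, or that their safety data are lost outright. The documents do not support that: events up to any Early Termination visit are collected, and serious events and AESIs have partial cover afterwards.

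A reader might also want a percentage of follow-up visits lost, or to say that every lost visit belongs to a subject with a bad course. No discontinuation rate is given, and the withdrawal reasons include subject request, protocol violation, non-compliance and loss to follow-up.

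Leaving the study when standard therapy begins is an explicit design choice, and later adverse events are harder to attribute. Removal in follow-up also does not hide the time-to-worsening event, because the trigger for removal is that same 1-point rise. For subjects who completed treatment, the Week 16 visit is already past. These points stand and limit the concern. They do not resolve the conflict over who is followed.

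**Conclusion.** The conflict is in the current text. Study Design Overview and Procedures follow all subjects, Drug Supply follows only those not discontinued, and the removal rules alternate between leaving the study and stopping treatment. For subjects who worsen, the end of scheduled visits is explicit. For subjects stopped for harm, it depends on the section applied.

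The size is up to 4 of 4 follow-up visits for a stop on treatment, at most 3 of 4 for removal in follow-up, and the Week 16 GPG score for removal before Week 16. These counts rest on the visit schedules in Tables 3 and 4 and on reading removal from the study literally. The total effect on the trial cannot be stated, because it depends on an unknown number of discontinuations. The point is worth correcting because the loss is likely to be related to outcome and the remedy is cheap. It does not invalidate the design.

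**What to change.** - Reconcile Study Design Overview, Procedures, Post-Spesolimab Follow-up Phase, Discontinuation of Treatment and Withdrawal of Subjects (with its Stopping Rules) and Investigational Drug Supply.
- Define two separate events, stopping study drug and leaving the study, and say at each removal rule which one is meant.
- State that, for data collection only, adverse events are recorded through 16 weeks after the last dose for every consenting subject, whatever therapy follows, and that later therapy is recorded with its start date.
- State that the Week 16 GPG score is obtained, where not yet reached, for every consenting subject who stops early.
- State that the Early Termination visit also applies when the investigator discontinues the subject.
- Tie the SAE and AESI reporting window to the same 16 weeks, so that it no longer depends on which section is applied.

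No treatment, rescue or stopping rule needs to change, and none is proposed here. The cost is protocol wording plus, for each early stop, a few visits already in Tables 3 and 4 or adverse event contacts in their place. Events after new therapy starts will be harder to attribute, so tabulate them separately from events before it.

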Demographics and Other Baseline Characteristics

Descriptive statistics of demographics and other baseline characteristics of patients will be summarized with mean, median, and standard deviation for quantitative outcomes, and frequency and percentage tables for categorical outcomes.. Other baseline characteristics include sex, age, height, weight, vital signs, duration of PG, history of pathergy or PG trigger (if known), concurrent diagnoses from medical history and indications for concomitant medication, concomitant medication, and previous PG treatments.

Target Lesion Measurement and Digital Image Assessments

Size of target PG lesion will be approximated at each visit by measuring the length, width and depth of the lesion. Target lesion will also be analyzed using Image J software to obtain a more precise surface area of each lesion using digital photographs taken at each visit.

Analysis of Primary Endpoint

We will compare the proportion of patients achieving one-point decrease in target lesion GPG score at Week 16 with a constant p=0.10. Clopper-Pearson 90% confidence interval will be estimated.

Analysis of Secondary Endpoints

- One sided Clopper-Pearson 90% confidence intervals will be estimated for the proportion of patients achieving re-epithelization (GPG Severity Score of 0) at Visits 3, 4, 5, 6, 7, 8, and 9
- We will apply a two-sided paired t-test to evaluate significance of the mean difference of GPG score at Week 16 versus Week 0.
- Mean patient reported scores of pain (Pain VAS) and quality of life (DLQI) at baseline will be compared to those at Week 16 and treatment termination using the student's t- test to compare between subject's pre and post-treatment scores.
- One sided Clopper-Pearson 90% confidence intervals will be estimated for the proportion of patients with recurrence or worsening of PG lesions from point of complete re-epithelization or spesolimab cessation at end of treatment visit (Week 28 or Week 26 depending on dosing frequency).

Interim Analysis

An interim analysis will be performed after the first 10 subjects complete Week 16. We will continue enrollment during this time. Proportion of patients achieving one-point GPG score decrease will be reported. Changes from baseline at Week 16 in the PG lesions (number, size, GPG score) will be evaluated and reported. Enrolled subjects will continue to receive treatments during this time.

Data Transfer and Management

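### The sample-size sentence is inconsistent: with 20 patients, a 10% constant and a one-sided 2.5% test, a 36.6-point difference gives 95.9% power, not 81%.

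*Combined protocol and SAP*

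**What the plan says.** The Sample Size paragraph under Statistical Considerations gives the trial's only quantitative argument for 20 patients. After a remark that no formal power calculation was made, it states that "a sample size of n=20 subjects allows 81% power at 2.5% significance for a one-sided binomial test". The effect that this refers to is worded as "to detect at Week 16 a difference of 36.6% in the proportion of GPG success compared to a constant set to be equal to 10" per cent. The constant is explained by an earlier infliximab trial in which "a group of 17 PG placebo-treated patients showed 6% response at Week 2".

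The Analysis of Primary Endpoint paragraph uses the same null value. It compares the proportion of patients "achieving one-point decrease in target lesion GPG score at Week 16 with a constant p=0.10" and adds a 90% Clopper-Pearson interval. It does not say whether that interval is one- or two-sided, states no significance level, and sets no number of responders that would count as success. The Study Design Overview describes enrolment as up to 20 patients.

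**The concern.** Sample size, null rate, test, level and difference together fix the power of a one-sample binomial test. Nothing is left to choose, so the stated 81% can be checked directly, and it does not come out.

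The stake is how readers understand the effect the trial can detect. Taken at its word, the sentence says that a true response rate of 46.6% is needed for about 80% power. Under the plan's own test, a rate of about 37% is enough. No other part of the document states an alternative response rate that would put the reader right.

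A related gap affects the reporting of the primary result. The power statement uses a one-sided 2.5% level, while the analysis paragraph offers a 90% interval. For at least one possible result the two lead to different conclusions.

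**Working it through.** **Inputs.** From Sample Size: n = 20; one-sided binomial test at 2.5%; null rate p0 = 0.10; stated difference 0.366; stated power 81%. From Analysis of Primary Endpoint: p0 = 0.10 again, and a 90% Clopper-Pearson interval.

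**Step 1: rejection region.** Take the smallest r with P(X ≥ r | 20, 0.10) ≤ 0.025.
- P(X ≥ 5) = 0.0432, which is too large.
- P(X ≥ 6) = 0.0113, which is admissible.

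The 2.5% test therefore rejects at 6 or more of 20, and its actual size is 1.1%.

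**Step 2: try to reproduce the stated power as worded.** The alternative is p1 = 0.10 + 0.366 = 0.466, and power is P(X ≥ 6 | 20, 0.466) = **95.9%**. The plan says 81%, about 15 points lower.

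**Step 3: could another method give 81%?** At p1 = 0.466, n = 20 and one-sided 2.5%:

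| Method | Power |
|---|---|
| Exact binomial | 95.9% |
| Score normal approximation | 98.2% |
| Score with continuity correction | 97.0% |
| Arcsine | 97.0% |
| Wald | 90.7% |

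For example, the score approximation is Φ[(p1 − p0 − 1.96·s0)/s1], with s0 = √(0.10 × 0.90/20) = 0.0671 and s1 = √(0.466 × 0.534/20) = 0.1115. This is Φ[(0.366 − 0.1315)/0.1115] = Φ(2.10) = 98.2%.

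Other settings do not help:
- Halving the level to one-sided 1.25% gives 85.1% to 97.3% across these methods.
- Keeping the 36.6-point difference and moving the null rate between 6% and 50% gives exact power of 89.8% to 96.9%.
- Moving the cut-off to 7 gives 89.8%. Moving it to 8 gives 79.2%, but that test has a size of 0.04% and is not a 2.5% test.

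**Step 4: read 36.6% as the response rate.** Now p1 = 0.366, and the difference is 0.366 − 0.10 = 0.266. Exact power is P(X ≥ 6 | 20, 0.366) = **79.9%**. This is close to 81% but not equal to it. Solving P(X ≥ 6 | 20, p1) = 0.81 gives p1 = 0.370, a difference of 27.0 points. The approximations at p1 = 0.366 do not give 81% either: score 89.4%, continuity-corrected 84.5%, arcsine 83.5%, Wald 69.5%.

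**Step 5: compare the 2.5% test with the 90% interval.** The Clopper-Pearson lower limit L for 5 of 20 solves P(X ≥ 5 | 20, L) = tail.
- Two-sided 90% interval (tail 0.05): L = 10.4%.
- One-sided 90% interval (tail 0.10): L = 12.7%.

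Both limits lie above 10%. Yet the one-sided p-value for 5 of 20 is 0.0432, so the 2.5% test does not reject. A result of 5 of 20 would look positive by the interval and negative by the test.

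**The case against.** The strongest reply is that the paragraph itself disclaims a formal power calculation. On that view the figures only illustrate, in an open-label proof-of-concept trial, what 20 patients can show, and n does not depend on them. This is fair as far as impact goes. At face value the sentence understates its power (95.9% against 81%). With 36.6% as the rate, power is still about 80%. A reader might infer that 20 patients are too few; neither reading supports that. But the disclaimer does not make the figure right, since the same sentence goes on to state power, level, sidedness, test and effect.

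A second reply is attrition. With a literal 36.6-point difference, power is 80.6% at 13 evaluable patients. The sentence, however, says 20 subjects, and the section states no dropout allowance.

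Two stronger readings are tempting, and the documents support neither:
- **That the sentence is shown to have swapped the rate for the difference, misstating the effect by 10 points.** Neither 36.6% nor 46.6% is given as a response rate anywhere, and the swap yields 79.9%, not 81%. It is a plausible explanation, but if the difference is right and the power is wrong, the effect is not misstated at all.
- **That 6 of 20 is the trial's success rule and 1.1% its type I error.** The primary analysis sets no responder threshold and no level. Six follows only from the 2.5% level in the power statement and from exactly 20 evaluable patients. With 17, for instance, the exact cut-off is 5, with size 2.2%.

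**Conclusion.** The power statement is wrong as written. Under its own inputs (20 evaluable patients, null rate 10%, exact one-sided binomial test at 2.5%), a 36.6-point difference gives 95.9% power, about 15 points above the stated 81%. This is arithmetic and does not depend on what the authors meant.

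The cause is an inference. That 36.6% is the alternative rate, with a 26.6-point difference and 79.9% power, is likely, but the sponsor has to confirm it. Only if it is confirmed has the detectable difference been overstated by 36.6 − 26.6 = 10 points.

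The mismatch between the 2.5% test and the 90% interval is a separate matter of consistency. It affects how a result of 5 of 20 would be reported, whether the interval is one- or two-sided.

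**What to change.** Check the source calculation, then replace the sentence with one that gives the null rate, the alternative rate and the difference separately. If the likely reading is confirmed, this would serve:

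*With n = 20, an exact one-sided binomial test at the 2.5% level against 10% rejects with 6 or more responders (actual size 1.1%). It has about 80% power if the true response rate is 36.6% (26.6 percentage points above 10%), and 96% power if it is 46.6%.*

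If 81% is to be kept, the matching alternative rate is about 37.0%.

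In Analysis of Primary Endpoint, state the level of the comparison with 0.10 and whether the interval is one- or two-sided, and choose the two so that they agree. The cut-off of 6 should be presented as a property of the 2.5% test with 20 evaluable patients, not added as a success rule that the analysis section does not contain.

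The cost is one rewritten sentence and a short clarification. Sample size and trial conduct stay as they are.
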